12.3.2. Data items to be collected

The following items are collected:

- **Demography and basic information:** Date of birth, gender, country of origin, ethnicity, height, weight, date of first HIV-1 positive test and mode of HIV-1 transmission.
- Laboratory data: HIV VL at all points of testing, CD4 count where available, hepatitis C status, hepatitis B serology, as well as routine laboratory data that describe the function of the kidneys and liver. Biomarkers of metabolic disease will also be collected.
- Medical treatment: Current HIV treatment regimen, prior ART regimen, number of HIV drugs and drug classes used in the past, year of first treatment regimen. Medical treatment related to co-infections and co-morbidities.
- Clinical events: Medical history and any interim clinical events (including AIDS, myocardial infarction, stroke, kidney failure, liver failure, cancer, bone fractures etc).
 Interim medical events will be assessed for seriousness and relatedness (an adverse reaction that may be possibly, probably or definitely related to the injections).

12.3.3. Participant questionnaire

An on-line participant questionnaire will be administered at baseline, and again at months 6 and 12 with both individuals on the injectable regimen and oral comparator. The participants on LA CAB+RPV will complete both sections of the questionnaire (LA CAB+RPV experience and HIV Patient Reported Outcome Measures), whereas those on oral ART will only complete the HIV PROM section. Where individuals are unable to use the on-line questionnaire a paper-based self-administered or research staff-administered questionnaire will be used. The questionnaire will be piloted and refined through a public participant involvement process.

Participants who complete a questionnaire will be remunerated with a shopping voucher to compensate for their time and effort.

12.3.4. Schedule of Activities

The following activities will take place for PLWH enrolled in the prospective cohort study.

Table 1. Schedule of Activities for Participants

·	individual baseline M0*	Individual month 6 (+/- 2 months)	Individual month 12 (+/- 2 months)
Informed consent process	Х		
ROUTINELY COLLECTED CLINIC DATA			
Baseline characteristics, height	X		
Comorbidities	Х	Х	Χ
HIV / ART history	Х		
HIV VL (all interim VLs collected)	Х	X	Χ
CD4+ T cell count (if available)	Х	X	Χ
Creatinine, eGFR, HbA1c, lipids, ALT, weight (if available)	X	X	X
Interim medical events requiring medical attention/treatment		X	X
QUESTIONNAIRES			
Participant questionnaire: • Section A: LA CAB+RPV treatment experience and preference • Section B: HIV PROM (oral comparator group only complete section B)	Х	X	Х
QUALITATIVE			
In-depth interviews (~n=3 at each site)		X	

^{*}Individuals who have been switched to LA CAB+RPV during the 6 months prior to the clinic site being opened for enrolment are eligible to join the prospective cohort study for the collection of routine clinic data. Their individual baseline is the date that they were switched to LA CAB+RPV.

eGFR = estimated glomerular filtration rate, ALT = alanine transaminase, HbA1c = haemoglobin A1c, HIV VL = HIV viral load, HIV PROM = HIV patient reported outcome measures

Approximately three healthcare workers from each participating clinic will be asked to complete a single questionnaire and engage with an interview / focus group discussion.

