	 4. FIDELITY: To describe the fidelity of regimen delivery and associated monitoring compared to intended use in BHIVA guidelines 5. EFFECTIVENESS: a. To characterise the UK-wide population who are switched to LA CAB+RPV and indications for switch b. To describe virological and clinical outcomes at one year of therapy in those on LA CAB+RPV and in those remaining on oral ART (demographically similar but not eligible for LA ART) c. To identify where actionable adjustments to implementation can be made to optimise overall adoption, sustainability and effectiveness of LA CAB+RPV 	
Primary outcome	1. ADOPTION:	
measures	a. Proportion of clinical cohort eligible for LA CAB+RPV according to BHIVA guidance	
	b. Proportion of eligible adults offered/discussed a switch to LA CAB+RPV	
	c. Proportion who accept the switch to LA CAB+RPV	
	d. Proportion who remain on LA CAB+RPV at one year and	
	reasons for switching off the regimen	
Design	This is a mixed methods, non-interventional, multi-centre,	
	prospective observational study with a nested qualitative	
Deputation	component at UK NHS HIV treatment centres.	
Population	Approximately 10-20 adults receiving LA CAB+RPV and 5-10 matched controls on oral ART will be included from each	
	participating centre	
Duration	Each participant in the observational cohort study will contribute	
Daration	at least 1 year of longitudinal data to the study.	
	The total duration of the study at each participating HIV centre	
	will be 2 years to allow time for recruitment and follow-up.	
	The total duration of the study at the Coordinating Centre will be	
	3.5 years to allow time for study set up followed by data	
	collection, cleaning and analysis.	
Statistical methods	This is primarily a descriptive study. Descriptive statistics will be	
	·	
Sample size		
Jumpic 312C	·	
	adults who remain on oral ART as the comparator population.	
Sample size	used explain the demographics, clinical and treatment characteristics of all participants (age, BMI, race/ethnicity, comorbidities, ART history). Data will be presented as summary statistics as appropriate (mean, median, standard deviation, IQR, maximum and minimum for continuous measurements, and numbers and proportions for categorical measurements). Across all study sites the aim is to recruit a minimum of 150 adults receiving LA CAB+RPV into the prospective cohort study and ~50 adults who remain on oral ART as the comparator population	

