9.2. Secondary Objectives

2. ACCEPTABILITY:

- a. To explore the acceptability of LA CAB+RPV amongst PLWH and health care workers delivering the regimen through a participant questionnaire, healthcare practitioner questionnaire and qualitative research.
- b. To compare patient-reported outcomes including quality of life, treatment satisfaction and treatment preference in those on LA CAB+RPV compared to those who remain on oral ART (demographically similar but not eligible for LA ART)

3. FEASIBILITY:

- c. To describe the feasibility of using the regimen from a clinical and patient perspective through outcomes in the participant and healthcare practitioner questionnaires
- d. To explore barriers and facilitators to effective implementation of the LA CAB+RPV regimen
- **4. FIDELITY:** To describe the fidelity of regimen delivery and associated monitoring compared to intended use in BHIVA guidelines

5. EFFECTIVENESS:

e. To characterise the UK-wide population who are switched to LA CAB+RPV and indications for switch

- f. To describe virological and clinical outcomes at one year of therapy in those on LA CAB+RPV and in those remaining on oral ART (demographically similar but not eligible for LA ART)
- g. To identify where actionable adjustments to implementation can be made to optimise overall adoption, sustainability and effectiveness of LA CAB+RPV

10. Outcome Measures

There are no interventional components to the study. Service-specific approaches to implementation of LA CAB+RPV in use at the study sites at study outset will be described, contrasted and compared.

Objective	Outcome measures	
Implementation outcomes		
ADOPTION 1. To quantify the adoption cascade	 a. Proportion of clinical cohort eligible for LA CAB+RPV according to BHIVA guidance b. Proportion of eligible adults offered/discussed a switch to LA CAB+RPV c. Proportion who accept the switch to LA CAB+RPV d. Proportion who remain on LA CAB+RPV at one year and reasons for switching off the regimen 	

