11.1.1. Observational study using routinely collected clinic data

The study will capture data from HIV-1 positive adults receiving long-acting cabotegravir and rilpivirine as part of their treatment regimen. All HIV-1 positive adults (≥ 16 years) who initiated long-acting cabotegravir and rilpivirine-based ART any time from 6 months prior to study site initiation will be eligible to be included in this study. A demographically similar comparator group on oral ART will also be invited to join the study. Routinely collected medical data from eligible and consenting participants' medical records will be extracted at key intervals, as laid out in the Schedule of Activities (see section 12.3.4), and entered into an electronic data capture system (Research Electronic Data Capture, REDCap). Variables of interest include demographic data, HIV treatment history, laboratory findings, which are all collected routinely in line with the BHIVA monitoring guidelines.

The total duration of patient follow-up is at least 1 year from the time of enrolment. The final analysis will be conducted following database lock after the last study participant has reached the 12 months treatment milestone and all data queries have been resolved.

Patients who received LA ART outside of the BHIVA criteria e.g. on compassionate grounds are of interest and can be included in the prospective study; the reasons for BHIVA criteria ineligibility and outcomes (duration of therapy, virological and clinical) will be described.

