12.3. Prospective observational study

12.3.1. Collation of routinely collected clinic data

Routine blood testing is performed as part of routine clinical care per the BHIVA HIV Monitoring Guidelines [9]. No research blood testing is performed. Routinely collected clinic data from the participants in the LA CAB+RPV group and oral ART comparator group will be submitted by the participating clinic investigator (research nurse or research assistant) at

baseline, 6 and 12 months via a REDCap case report form. HIV viral load will be collected at every time point that it is measured from the time of participant enrolment.

It is possible to include data on consenting adults who started the injectable regimen up to 6 months prior to the clinic being activated as a study site. These individuals will not be asked to complete the participant questionnaires but their routinely collected clinic data is still valuable to the study objectives.

Continuation of the cohort study period for a longer duration may be possible if funding is made available for cohort and data management. Participants would be contacted to ask whether there are willing for their routinely collected clinic data to be shared beyond the initial 12-month data collection period. This would not involve any additional procedures for the participant.

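### The final data-collection window opens at month 10, so the schedule does not secure the promised year of follow-up for interim events and other cumulative 12-month items

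*Protocol*

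**What the plan says.** Table 1 in Section 12.3.4 has three collection points for cohort participants: baseline, month 6 and "Individual month 12 (+/- 2 months"). Interim medical events are ticked only in the month-6 and month-12 columns. Section 12.3.1 says that sites submit routine clinic data at "baseline, 6 and 12 months via a REDCap case report form", and treats anything "beyond the initial 12-month data collection period" as a possible extension that would depend on new funding and on asking participants again.

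Against this, the Duration entry of the Protocol Summary says that each cohort participant contributes "at least 1 year of longitudinal data to the study", and Section 11.1.1 says: "The total duration of patient follow-up is at least 1 year from the time of enrolment". Section 10 defines HIV-related medical events and virological failure at 12 months and counts bridging courses per patient per year. Section 17 adds a description of how many participants discontinue LA CAB+RPV and why.

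Two further statements bear on the point. Section 12.3.1 says: "HIV viral load will be collected at every time point that it is measured from the time of participant enrolment". Section 11.1.1 places the final analysis after "database lock after the last study participant has reached the 12 months treatment milestone".

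**The concern.** A symmetric window is reasonable for something measured on a day, such as a CD4 count or a questionnaire. It suits a cumulative outcome less well, because the date on which the form is completed decides how much time was observed. A form completed at month 10 contains no events from months 10 to 12. A form completed at month 14 may contain events from beyond the year. Both are compliant, and both would be reported as 12-month results.

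At stake are the completeness of the safety and effectiveness description for the LA and oral groups, and the comparability of exposure between sites that collect early and sites that collect late. An analysis plan can discard events after month 12 if they are dated. It cannot recover events between month 10 and month 12 that were never extracted.

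**Working it through.** **Inputs from the Protocol.** Last collection: month 12, plus or minus 2 months (Table 1). Stated minimum follow-up: 12 months (Summary; Section 11.1.1). LA sample size: 150 (Section 17). The Protocol gives no event rate and no distribution of collection dates, so both are assumed below.

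**1. The stated minimum.** Earliest compliant final collection: 12 − 2 = 10 months. Latest: 12 + 2 = 14 months. The 12-month minimum is therefore not reproduced by the schedule. The possible shortfall is 2/12 = 16.7% of the year, and exposure can differ between participants by a factor of 14/10 = 1.4.

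**2. Whether other text closes the gap.** Section 12.3.1 schedules no submission after the 12-month form. Locking the database after the last participant's 12-month milestone leaves time for an early form to be updated, but no text tells a site to do so. Viral loads are to be collected whenever measured, which largely protects virological failure, although no end date is given for entering values that arise after an early form. Interim events have no equivalent provision.

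**3. Size if everyone were collected at month 10.** With a constant hazard, risk observed by month 10 = 1 − (1 − p)^(10/12), where p is the true 12-month risk (assumed).

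| Assumed p | Shown at month 10 | Expected with event in 150 at month 12 | Missed |
|---|---|---|---|
| 2% | 1.67% | 3.0 | 0.5 |
| 5% | 4.18% | 7.5 | 1.2 |
| 10% | 8.41% | 15.0 | 2.4 |
| 20% | 16.97% | 30.0 | 4.6 |

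About 15% to 17% of those with an event would be missed. This is the extreme case.

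**4. Less extreme cases.** If a quarter of the 150 were collected at month 10 and the rest were complete, p = 10% gives 0.25 × 2.39 = 0.6 people missed, and p = 20% gives 1.1. If collection dates were uniform over months 10 to 14 and events were counted only to month 12, half of participants would close early. Their mean shortfall would be 1 month, so the overall mean is 0.5 × 1 = 0.5 months, or 4.2% of the year. For p = 10% the figure shown would be 9.6%, again about 0.6 people missed.

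**5. The late half of the window.** If all were collected at month 14 with no cut-off, p = 10% would show as 1 − 0.9^(14/12) = 11.6%, an excess of about 2.3 people. With dates uniform over 10 to 14 months and no cut-off, the average is 10.0%, so the two halves cancel. The average error thus depends on when sites collect and on whether a cut-off is applied, and the Protocol fixes neither.

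**The case against.** **Table 1 sets a window for a form and does not say that follow-up ends there.** This stands in part. With the one-year minimum and the timing of database lock, a careful site could read the Protocol as requiring an update. But nothing instructs it to, and a month-10 form is compliant as written.

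**A reader might infer that the primary one-year retention figure is overstated.** The documents do not support this. The outcome "Proportion who remain on LA CAB+RPV at one year and reasons for switching off the regimen" is counted by clinics from the registry dataset (Sections 11.1.5 and 12.6), which asks for at least one year on the regimen. Table 1 does not govern that count. Only the cohort discontinuations of Section 17 are exposed.

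**A reader might infer a bias in one direction.** That holds only if outcomes are cut off at month 12, a rule the Protocol does not state. Without it, late collections add events. Under uniform dates, persistence of 85% at one year would average 85.0%. With the cut-off it would read 85.6%.

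**A reader might infer that the two-year site life forces late joiners into early collection.** It does not. A participant starting at site month 12 still has 24 − 12 = 12 months, exactly the required period, though with no slack afterwards.

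**Virological failure and bridging are less exposed.** Agreed. All viral loads are to be collected, and bridging is expressed per patient per year, so it can be scaled to exposure if the closing date is recorded.

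**The effect is small in a descriptive study.** Also fair. At 10% risk and n = 150 the standard error is √(0.1 × 0.9/150) = 2.4 percentage points, larger than the 1.6-point shift in the extreme case. How partly observed participants are counted is a matter for the analysis plan and is not criticised here.

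**Conclusion.** The Protocol states a follow-up minimum of one year that its schedule does not secure. Cumulative cohort items can be observed for 10 to 14 months and reported as 12-month results, with up to 16.7% of the year missing for participants collected early. The gap matters most for interim medical events and cohort discontinuations, and less for bridging and virological failure. Primary retention is outside it.

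The numerical effect is modest. In the extreme case about 2.4 of 15 people with an event are missed at an assumed 10% risk; under plausible date spreads it is below one person. These figures rest on a constant hazard and assumed risks. The direction of the average error cannot be stated from the Protocol. The point is worth correcting because unextracted events cannot be restored at analysis, and because the data come from clinic records, so waiting for the full year needs no extra visit or test.

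**What to change.** In Table 1 and the eCRF instructions, require interim medical events, bridging courses, treatment status and viral loads to be extracted through 12 completed months from individual baseline. Either the final extract is made on or after that date, or an earlier form is updated to it. State that cumulative outcomes are counted only up to the 12-month date.

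Keep the plus or minus 2 months for point measures (snapshot viral load, CD4, eGFR and other laboratory values) and for the questionnaires. State that the final records extract for late joiners may be made shortly after site month 24.

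The cost is a line in Table 1 and matching text in the eCRF manual. Some final forms will arrive up to 2 months later, and sites that recruit up to month 12 may need a short period of access to records after their two years.

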12.4. Nested qualitative study

12.4.1. Participant in-depth interview

A subset of PLWH in the prospective cohort study at each site will be approached to consent for an in-depth interview about their experiences with the injectable regimen after receiving approximately 6 months of injectable treatment. The in-depth interviews will be conducted by a research assistant from Brighton and Sussex Medical School at the University of Sussex. An additional consent process will be undertaken (see section 21.3) and consenting individuals will be interviewed on-line where possible. Interviews will take a maximum of 1 hour and will be audio-recorded then transcribed and anonymised for analysis. It is anticipated that interviewing approximately 3 individuals at each site will reach thematic saturation. Where interviews cannot be conducted on-line then a member of the research team can support an in-person interview. A study participant will only be interviewed once during their follow-up period. Anyone interviewed will be remunerated with a £20 shopping voucher to compensate for their time and effort.

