9.1. Primary Objective

1. ADOPTION: To describe the strategies being deployed in different UK HIV services to deliver LA CAB+RPV and to quantify the adoption cascade in terms of what proportion of each clinic cohort are: a) eligible for LA CAB+RPV in accordance with BHIVA

guidelines; b) have a switch to LA CAB+RPV discussed; c) accept a switch to LA CAB+RPV; and to ascertain reasons for attrition at each step of the cascade (Fig. 1).

[figure not shown]

Figure 1. Adoption cascade

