11.1.3. In-depth interviews with subset of participants

A subset of participants (2-3 per site) will be invited to an in-depth interview where a topic guide of open-ended questions will facilitate a deeper understanding of the participant's experiences and perceptions. Qualitative data from in-depth interviews will be audio-recorded and transcribed for thematic analysis. Participants who are interviewed will be

reimbursed for their time with a £20 shopping voucher. This is in addition to the reimbursement given for completing questionnaires.

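### In-depth interviews require about 6 months on the injections, so participants who stop before about month 4 have no route to an interview and the patient themes on barriers lean towards people who stayed

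*Protocol*

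**What the plan says.** Four places in the protocol determine who can be interviewed.

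- Section 12.4.1 approaches a subset of the cohort at each site for an interview about "their experiences with the injectable regimen after receiving approximately 6 months of injectable treatment", and adds: "A study participant will only be interviewed once during their follow-up period".
- Table 1 (section 12.3.4) has the row "In-depth interviews (~n=3 at each site", marked only in the month 6 column, which carries a window of 2 months either side.
- Section 11.1.3 states: "A subset of participants (2-3 per site) will be invited to an in-depth interview". It sets no minimum time on treatment and says nothing about people who have stopped.
- The protocol summary and section 17 plan 20-30 qualitative participants in total.

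No section provides an exit interview or directs sites to seek out discontinuers.

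On the side of the objectives, section 9.2 lists "To explore barriers and facilitators to effective implementation of the LA CAB+RPV regimen" under feasibility. The outcome table in section 10 (where this is objective 3b) names the qualitative work as its data source at both individual and service level. Objective 5c in the same table uses what is learned about barriers to propose changes that services can act on.

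**The concern.** Someone who gives up the injections after the first few visits met a barrier that proved decisive. An interview rule tied to about 6 months of treatment received passes over that person and samples those who got past the early difficulties. Selection on staying in treatment is then built into the only in-depth patient source for objective 3b.

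The selection has a direction. Section 8 expects high acceptability among those who switch, and interviewing people who have stayed for several months tilts the accounts the same way. The expectation in section 12.4.1 that about three interviews per site will reach thematic saturation is no safeguard: saturation among people who stayed says nothing about themes found only among people who left early. At stake is whether the patient-side account of barriers, and the advice to services built on it, covers early failure of the regimen for the individual.

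**Working it through.** The protocol gives no figure to reproduce here. The check is a reading of the interview rule against each possible course of treatment, followed by a short illustration of size.

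**1. Who the rule admits.** Table 1 alone does not require the interviewee to be on treatment; the condition comes from section 12.4.1. If 'approximately' there is read with the Table 1 window, the range is 6 - 2 = month 4 to 6 + 2 = month 8.

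| Course of treatment | Section 12.4.1 condition | Month 6 slot in Table 1 | Interview possible as written? |
|---|---|---|---|
| Stops before about month 4 | Not met | Falls due, but condition unmet | No |
| Stops at about month 4-6 | Arguably met | Within window | Arguably |
| Stops after month 6, before the interview | Met | Within window up to month 8 | Yes |
| Continues | Met | Within window | Yes |

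With one interview per person and no other slot, the first row has no alternative route. These people are still in the study: section 14 gives withdrawal of consent as the reason for leaving it, not stopping treatment.

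**2. Which objectives depend on the interviews.**

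- Objective 3b, individual-level barriers: yes, section 10 names the qualitative work as the source.
- Objective 5c: in part, since it reports lessons about barriers and facilitators.
- Primary objective (section 9.1): no. It sets out "to ascertain reasons for attrition at each step of the cascade", but the steps listed there are eligibility, discussion and acceptance, and sections 11.1.5 and 12.6 have the clinic record why a switch was not offered or was declined.
- Primary outcome 1d, "Proportion who remain on LA CAB+RPV at one year and reasons for switching off the regimen": no. Section 17 describes the number, proportion and reasons for discontinuation from cohort data.

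**3. Size, by assumption.** The protocol gives no early-stopping rate. With N = 150 long-acting participants (section 17) and an assumed proportion p stopping too early to be interviewed, the number outside the frame is N x p:

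- p = 2%: 150 x 0.02 = 3
- p = 10%: 150 x 0.10 = 15

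Over the 10-12 sites of section 11.2 this is between 3 / 12 = 0.25 and 15 / 10 = 1.5 people per site, so many sites may have none.

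**The case against.** A common interview point after several injections is a defensible choice for a small nested sample meant to explore experience of the regimen, and the protocol does not contradict itself here. Other sources also bear on barriers. Healthcare workers are interviewed about them (section 11.1.4), at any time during site participation (section 12.4.2), and they see the early stoppers. Participant questionnaires run at months 0, 6 and 12, and nothing says they end when treatment stops. Interviewees at month 6 may themselves have had late injections or oral bridging.

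Much of this stands, and it rules out three stronger readings that a reader might infer:

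- *Every interviewee must be a continuer.* The wording and the window can admit someone who stops at about month 4-5 or shortly after month 6.
- *The primary objective is compromised.* Reasons for attrition and for discontinuation come from the registry and the cohort data, not from the interviews.
- *Evidence on barriers would come only from people for whom the service worked.* The healthcare worker and questionnaire data are not restricted in that way.

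What survives is narrower. A recorded reason or a clinician's view is not the patient's own in-depth account. Section 12.3.3 gives the treatment-experience section of the questionnaire to participants on the long-acting regimen and does not say whether those who have stopped still complete it. Section 12.3.1 gives no questionnaire at all to people who started before site activation, so an early stopper among them would provide neither questionnaire nor interview.

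**Conclusion.** The point holds in limited form. As written, participants who stop before about month 4 cannot be interviewed, and the patient interview themes on barriers are selected towards people who stayed. Objective 3b is affected most and objective 5c through it; the primary proportions and the recorded reasons for attrition are untouched. The month 4 boundary rests on reading 'approximately' with the Table 1 window. The 3 to 15 people rest wholly on an assumed 2% to 10% early-stopping rate, but the case does not turn on that rate, since even a few such accounts would add information to a set of 20-30. This is an inexpensive improvement to the design rather than an error that invalidates a result.

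**What to change.** Amend section 12.4.1, section 11.1.3 and Table 1 so that the interview takes place 'at about month 6, or at or after discontinuation if earlier'. Add a sentence that early discontinuers will be purposively approached where they occur, across the study as a whole.

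Keep the total at 20-30 interviews, one per person. Use the existing separate interview consent (sections 12.2 and 12.4.1), since consent to the cohort does not cover the interview. Do not set a per-site quota: one reserved place out of 2-3 per site would take a third to a half of that site's interviews, and many sites may have no early discontinuer.

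The cost is protocol wording, a few fewer interviews with continuers and a less uniform interview time point. The report should therefore state how many interviewees had stopped, and when. No additional interviews or vouchers are needed.
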